11.1 Terms and definitions

- **M-protein:** synonyms include M-spike, monoclonal protein and myeloma protein, paraprotein, M-component.

Serum M-protein level is quantitated using densitometry on SPEP except in cases where the SPEP is felt to be unreliable.

- M-proteins migrating in the β -region (usually IgA M-proteins)
- Cases in which the M-spike is so large and narrow on agarose (some specimens >4 g/dL) that they underestimate the actual immunoglobulin level (by greater than 1500 mg/dL) due to technical staining properties of the agarose gel.
- Cases in which there are multiple peaks of same monoclonal protein (aggregates or dimers)

If SPEP is not available or felt to be unreliable (above examples) for routine M-protein quantitation, then quantitative immunoglobulin levels derived from nephelometry or turbidometry can be accepted, with the exception that quantitative IgG may not be used. However, this must be explicitly reported at baseline, and only nephelometry can be used for that patient to assess response. SPEP derived M-spike values and quantitative nephelometric immunoglobulin values cannot be used interchangeably.

Urine M-protein measurement is estimated using 24-h UPEP only. Random or 24 h urine tests measuring kappa and lambda light chain levels are not reliable and are not recommended.

FLC estimation is currently carried out using the serum FLC assay (Freelite, The Binding Site Limited, UK). Patients with kappa/lambda FLC ratio <0.26 are defined as having monoclonal lambda FLC and those with ratios >1.65 as having a monoclonal kappa FLC. The monoclonal light chain isotype is considered the involved FLC isotype, and the opposite light chain type as the uninvolved FLC type.

- **Response terms:** The following response terms will be used: stringent Complete Response (sCR), complete response (CR), very good partial response (VGPR), partial response (PR), Minimal Response (MR), stable disease (SD), and progressive disease (PD).

In addition, for each response category, there will be an “unconfirmed” response category, which will be for internal use, for the purpose of guiding decision making and test ordering. These designations will be applied at the time of the first measurement at which the quantitative aspect of the response category has been satisfied without the confirmation step having been satisfied. The designation “u” will precede the standard abbreviations, and will include usCR, uCR, uVGPR, uPR, uMR, uPD.

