11.5 Response and Progression

Criteria for response and progression are listed in Table 11.51. Progressive disease for all patients as defined in Table 11.51.

Table 11.51

CATEGORY	RESPONSE CATEGORY ^a
Stringent Complete Response (sCR) ^b	
 • CR as defined plus • Normal FLC ratio and • Absence of clonal PCs by immunohistochemistry or 2- to 4-color flow cytometryⁱ
Complete Response (CR) ^b	
 • Negative immunofixation of serum and urine^c and • Disappearance of any soft tissue plasmacytoma and • ≤5% PCs in Bone Marrow and • If the only measurable disease is FLC, a normal FLC ratio^d
Very Good Partial Response (VGPR)	
 • Serum and urine M-component detectable by immunofixation but not on electrophoresis^c or • ≥90% reduction in serum m-component and urine m-component <100 mg/24 h^c • If the only measurable disease is FLC, a ≥90% reduction in the difference between involved and involved FLC levels

CATEGORY	RESPONSE CATEGORY ^a
Partial Response (PR)	
 • If present at baseline, $\geq 50\%$ reduction of serum M-protein and reduction in 24-hour urinary M-protein or to < 200 mg/24hrs • If the only measurable disease is FLC, a $\geq 50\%$ reduction in the difference between involved and involved FLC levels • If the only measurable disease is BM, a $\geq 50\%$ reduction in BM PC's (provided the baseline PC's was $\geq 30\%$) • If present at baseline, $\geq 50\%$ reduction in the size of soft tissue plasmacytomas
Minor Response (MR)	
 • If present at baseline, $\geq 25\%$ but $< 49\%$ reduction of serum M protein and reduction in 24-hour urine M-protein by 50-89% which still exceeds 200mg/24 hours ^c and • If present at baseline, 25-49% reduction in the size of soft tissue plasmacytoma and • No increase in the size or number of lytic bone lesions (development of compression fracture does not exclude response)

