Progressive Disease (PD) ^{b, h}	
Increase of 25% from lowest value in any of the following ^{f, g}:
 
 • Serum M-component (absolute increase must be ≥ 0.5 mg/dL) AND/OR • Urine M-component (absolute increase must be ≥ 200 mg/24 hrs) AND/OR • If the only measurable disease is FLC, the difference between involved and uninvolved FLC levels (absolute increase must be > 10 mg/dL) AND/OR • If the only measurable disease is BM, bone marrow PC percentage (absolute increase must be $> 10\%$) ^e 
Or any one or more of the following:
 
 • Development of new bone lesion or soft tissue plasmacytoma or definite increase in the size of existing bone lesions or soft tissue plasmacytoma • Development of hypercalcemia (corrected serum calcium > 11.5mg/dL) that can be attributed solely to the PC proliferative disorder
Stable Disease (SD)	Not meeting criteria for sCR, CR, VGPR, PR, MR or PD

^a All response categories require two consecutive assessments (sCR, CR, VGPR, PR, MR, PD) made at anytime before the institution of any new therapy; sCR, CR, VGPR, PR, MR and SD categories also require no known evidence of progressive or new bone lesions if radiographic studies were performed. Radiographic studies are not required to satisfy these response requirements. Bone marrow assessments need not be confirmed. Each category, except for stable disease, will have a working subcategory of “unconfirmed” [prefix ‘u’] to designate first time point at which response category MAY have been achieved if confirmed.

^b CR patient will need to progress at the same level as VGPR and PR patients to be considered a PD. A positive immunofixation alone is not sufficient.

^c If more than one M protein spikes meet the criteria for measurable disease at baseline, then both need to be followed for response. Otherwise, only follow the measurable M protein spike for response.

^d In patients in whom the only measurable disease is by serum FLC levels: CR in such patients indicates a normal FLC ratio of 0.26-1.65 in addition to the CR criteria listed above.

^e Bone marrow criteria for PD are only to be used in patients without measurable disease by M protein and by FLC.

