^f A "25% increase" refers to M protein, FLC and bone marrow results and does not refer to bone lesions, soft tissue plasmacytoma or hypercalcemia. The lowest value does not need to be a confirmed value. If the lowest serum M-component is ≥ 5 g/dL, an increase in serum M-component of ≥ 1 g/dL is sufficient to define disease progression.

^g In the case where a value is felt to be a spurious result per physician discretion (for example, a possible lab error), that value will not be considered when determining the lowest value.

^h Progressive disease should be confirmed. However, treatment may be discontinued for progressive disease that is unconfirmed per physician discretion. In this case, an objective status of PD should be entered on the measurement form and progressive disease should be reported on the event monitoring form.

ⁱ Presence/absence of clonal cells is based upon the k/l ratio. An abnormal k/l ratio by immunohistochemistry requires a minimum of 100 plasma cells for analysis. An abnormal ratio reflecting presence of an abnormal clone is k/l of 4:1 or 1:2.

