12.0 Descriptive Factors

- 12.1 Parameters followed for hematologic response (pick one): serum monoclonal protein ≥ 1 g/dL and urine M-spike ≥ 200 mg/24 hours vs. serum monoclonal protein ≥ 1 g/dL only vs. urine M-spike ≥ 200 mg/24 hours only vs. serum immunoglobulin free light chain ≥ 10 mg/dL.

NOTE: Distinguish between SPEP measurement versus quantitative IgA measurement for serum monoclonal protein.

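### Table 11.51 is wrong as written in two operative definitions: the unit of the serum progression floor, and the light-chain difference in the FLC-only VGPR and PR rows

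*Combined protocol and SAP*

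**What the plan says.** Section 11.5 gives the table full authority over progression: "Progressive disease for all patients as defined in Table 11.51". For serum disease the table asks for a 25% increase over the lowest value, subject to a minimum: "Serum M-component (absolute increase must be ≥ 0.5 mg/dL".

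Footnote f, attached to the same row, deals with high nadirs (lowest value at least 5 g/dL). There a rise of 1 "g/dL is sufficient to define disease progression". Other serum M-protein figures are on that scale too:
- eligibility in 3.15 and measurable disease in 11.1 (1 g/dL);
- Table 11.21 (1 g/dL);
- the agarose caveat in 11.1, "M-spike is so large and narrow on agarose (some specimens >4 g/dL";
- the descriptive factor in 12.1, "g/dL only vs. urine M-spike".

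Elsewhere in Section 11, mg/dL is used for free light chains, calcium and the size of an immunoglobulin underestimate, not for an M-spike threshold.

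For patients whose only measurable disease is FLC, the VGPR row (at least 90%) and the PR row (at least 50%) both require a "reduction in the difference between involved and involved FLC levels". The progression row for the same patients uses "the difference between involved and uninvolved FLC levels", and 11.1 likewise describes the ratio or difference of involved and uninvolved chains.

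**The concern.** Both slips sit in rules that classify patients. An absolute floor stops a small rise from a low nadir counting as progression. At 0.5 mg/dL it has practically no effect, and the patients concerned are those with low nadirs, which include the deep responders this regimen is meant to produce. Progression dates feed PFS (16.324), and under 13.3 progression moves a patient to event monitoring.

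The FLC wording makes a response category impossible to compute. FLC-only patients are eligible under 3.15, and 11.1 says they are to be assessed by FLC criteria. They therefore count in the primary ≥VGPR proportion (16.311) and the ≥PR proportion (16.321).

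The practical risk is a CRF edit check or a response program that follows the table to the letter.

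**Working it through.** **Design figures.** The plan gives no calculated figure for this point. Its operating characteristics were reproduced to see whether anything there is disturbed. With b(x; n, p) the binomial probability, the chance of stopping early is the sum of b(x; 13, p) for x = 0 to 3. The chance of a positive result is the sum over x = 4 to 13 of b(x; 13, p) × P(Bin(24, p) ≥ 13 − x).
- At p = 0.25: positive 0.0920, stopping 0.5843 (plan: 0.092 and 0.584).
- At p = 0.45: positive 0.8560, stopping 0.0929 (plan: 0.856 and 0.093).

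Neither slip enters these sums.

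**Serum floor.** Inputs, all from Table 11.51: a 25% rise over nadir, and a floor of 0.5 in the printed unit.
- Conversion: 0.5 mg/dL ÷ 1000 = 0.0005 g/dL.
- Rise needed = max(0.25 × nadir, floor).
- The floor binds while 0.25 × nadir < floor. As printed: 0.0005 / 0.25 = 0.002 g/dL. On the g/dL scale: 0.5 / 0.25 = 2.0 g/dL.

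| Nadir (g/dL) | Rise needed, as printed (g/dL) | Rise needed, floor in g/dL | Ratio |
|---|---|---|---|
| 0.2 | 0.05 | 0.5 | 10 |
| 0.5 | 0.125 | 0.5 | 4 |
| 1.0 | 0.25 | 0.5 | 2 |
| 1.5 | 0.375 | 0.5 | 1.33 |
| 2.0 | 0.5 | 0.5 | 1 |
| 3.0 | 0.75 | 0.75 | 1 |

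From a nadir of 5 g/dL, footnote f applies in the same way under both readings.

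**Which serum-followed patients fall below 2.0 g/dL.** A reduction of at least 90% gives a nadir of at most 0.1 × baseline, which is below 2.0 for any baseline under 2.0 / 0.1 = 20 g/dL. A reduction of at least 50% gives at most 0.5 × baseline, which is below 2.0 for any baseline under 2.0 / 0.5 = 4 g/dL. The range therefore takes in VGPR patients and many PR patients. The documents give no baseline distribution, so a count cannot be derived.

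**FLC rows.** As printed, the quantity is involved − involved = 0 at baseline and at every later visit. The percentage reduction is (0 − 0) / 0, which is undefined for both the 90% and the 50% criterion. With involved − uninvolved, as in the progression row, both criteria can be computed.

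**The case against.** The strongest reply is that these are typing errors whose intent is plain. Footnote f supplies the serum scale, the FLC progression row and 11.1 supply the missing word, and Section 11.0 names the IMWG uniform criteria as the standard. An FLC check coded literally would fail visibly and would not misclassify anyone silently. PFS is a descriptive Kaplan-Meier estimate with no test or comparator. Footnotes a and h expect progression to be confirmed. Nothing shows that the CRF copied the error.

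Much of this stands, and it limits the weight of the point. It does not remove it. Section 11.5 makes the table itself operative. Confirmation is only partial protection: footnote h lets treatment stop on unconfirmed progression and has that recorded as progression, and footnote f says the nadir need not be a confirmed value.

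Three stronger readings are not supported:
- **A contradiction of footnote b.** That note says "CR patient will need to progress at the same level as VGPR and PR patients to be considered a PD". A reader might infer that the printed floor breaks it. It does not, because the floor applies identically to all three groups. The same note also says that a positive immunofixation alone is not enough.
- **A cap on patients affected.** Multiplying 37 by the design proportions gives 37 × 0.25 = 9.25 and 37 × 0.45 = 16.65, which a reader might take as an upper bound of about 9 to 17. These are expected four-cycle success counts at two assumed rates. Later ≥VGPR responders and PR patients with nadirs below 2 g/dL could add to them, while patients followed by urine or FLC only would not be exposed to the serum slip.
- **Demonstrated misclassification at very low nadirs.** The table above shows arithmetic thresholds. The documents give no reporting resolution for SPEP, so they do not show that the smallest rises would be measured.

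**Conclusion.** The point holds: Table 11.51 is wrong as written in two operative definitions and should be corrected, although the intent of both can be recovered from neighbouring text.

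The serum floor is smaller by a factor of 1000 than the same figure on the g/dL scale used in its own footnote. Read literally, it could bring progression dates forward in serum-followed patients with nadirs below 2.0 g/dL, and so shorten the descriptive PFS. The FLC-only VGPR and PR rows cannot be evaluated as printed. That reaches the primary ≥VGPR and secondary ≥PR endpoints, for FLC-only patients alone.

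The number of patients affected by either slip, and the shift in PFS, cannot be computed from the documents. A reader might infer that the trial's design or primary conclusion is undermined. It is not: sample size, alpha, power and the rule of at least 13 successes in 37 are untouched. The conclusion rests on the document's internal inconsistency and on a literal reading of the table. It assumes nothing about assay precision and does not rely on the outside criteria that the protocol cites.

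**What to change.** In Table 11.51, reconcile the unit of the serum progression floor with footnote f and with the g/dL scale of the other serum M-protein thresholds. In the FLC-only VGPR and PR rows, replace the second mention of the involved chain with the uninvolved chain, to match the progression row and 11.1. Then check that the CRF fields, edit checks and response and PFS programs match the corrected table.

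The cost is one unit, one word in each of two rows, and that check. No new data and no design change are needed.

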12.0 Descriptive Factors

- 12.1 Parameters followed for hematologic response (pick one): serum monoclonal protein ≥ 1 g/dL and urine M-spike ≥ 200 mg/24 hours vs. serum monoclonal protein ≥ 1 g/dL only vs. urine M-spike ≥ 200 mg/24 hours only vs. serum immunoglobulin free light chain ≥ 10 mg/dL.

NOTE: Distinguish between SPEP measurement versus quantitative IgA measurement for serum monoclonal protein.

13.0 Treatment/Follow-up Decision at Evaluation of Patient

13.1 Categories of response

Patients who are sCR, CR, VGPR, PR, MR, or (or usCR, uCR, uVGPR, uPR, uMR) will continue treatment per protocol. Patients will go off treatment to event monitoring if an MR is not seen after 2 cycles and a PR is not seen after 4 cycles. Confirmation of MR or PR is not required.

13.2 Patients who receive transplant

Patients who receive a transplant will go to event monitoring per Section 18.0. The transplant should be reported on the event monitoring form.

13.3 Progressive disease or alternate therapy

Patients who develop progressive disease or start alternate therapy will go to the event-monitoring phase per Section 18.0.

13.4 Off protocol for reasons other than PD

Patients who go off protocol treatment for reasons other than PD will go to the event-monitoring phase per Section 18.0.

13.5 Discontinuation for unacceptable AEs

Patients who discontinue therapy for an unacceptable adverse event(s) will be followed until resolution or stabilization of the AE(s).

13.6 Criteria for Patient Withdrawal from Study Treatment

Patients may be withdrawn from the study for the following reasons:

- Progressive multiple myeloma
- Patient refuses further treatment on the trial
- Patient develops an intercurrent illness that precludes further participation, or requires a prohibited concomitant treatment
- The Investigator withdraws the patient in the patient's best interests
- Patient is lost to follow-up (defined as the inability to contact the patient on 3 separate occasions)
- Administrative reasons (e.g., the patient is transferred to hospice care)
- An adverse event, which in the opinion of the Investigator, precludes further trial participation

All attempts should be made to complete the End of Study procedures if a patient withdraws from the trial early.

13.7 Criteria for Study Discontinuation

The study may be temporarily or permanently discontinued at any site and at any time. Reasons for study discontinuation may include, but are not limited to, the following:

- Safety concerns
- Poor enrollment
- Non-compliance with the protocol, Good Clinical Practice guidances or other regulatory requirements by the Investigator(s)
- Request to discontinue the trial by a regulatory or health authority or an IRB
- Manufacturing difficulties/concerns

All Investigators and the requisite regulatory authorities will be notified if the study is suspended or terminated for safety reasons. In the case of such termination, the Investigator will notify the IRB.

13.8 Patient Ineligible

A patient is deemed *ineligible* if after registration, it is determined that at the time of registration, the patient did not satisfy each and every eligibility criteria for study entry. The patient may continue treatment off-protocol at the discretion of the physician as long as there are no safety concerns, and the patient was properly registered. The patient will go directly to the event-monitoring phase of the study (or off study, if applicable).

- If the patient received treatment, all data up until the point of confirmation of ineligibility must be submitted. Event monitoring will be required per Section 18.0 of the protocol.
- If the patient never received treatment, on-study material and the End of Active Treatment/Cancel Notification Form must be submitted. No further data submission is necessary.

13.9a Patient major violation

A patient is deemed a *major violation*, if protocol requirements regarding treatment in cycle 1 of the initial therapy are severely violated that evaluability for primary end point is questionable. All data up until the point of confirmation of a major violation must be submitted. The patient will go directly to the event-monitoring phase of the study. The patient may continue treatment off-protocol at the discretion of the physician as long as there are no safety concerns, and the patient was properly registered. Event monitoring will be required per Section 18.0 of the protocol.

13.9b Patient cancel

A patient is deemed a *cancel* if he/she is removed from the study for any reason before any study treatment is given. On-study material and the End of Active Treatment/Cancel Notification Form must be submitted. No further data submission is necessary.

14.0 Body Fluid Biospecimens

14.1 Summary Table of Research Blood and Body Fluid Specimens to be collected for IRB #521-93 :

Correlative Study (Section for more information)	Mandatory or Optional	Blood or Body Fluid being Collected	Type of Collection Tube (color of tube top)	Volume to collect per tube (# of tubes to be collected)	Baseline	Cycle 1	Cycle 2	Cycle 3	Cycle 4	Cycles ≥5	Process at site? (Yes or No)	Temperature Conditions for Storage /Shipping
						End of cycle	End of cycle	End of cycle	End of cycle			
PDL1 expression (14.41)	Mandatory	Marrow	ACD (yellow)	6 ml per tube (3)	X				X	Any subsequent marrow	No	Kool-pak
Immune markers (14.42)	Mandatory	Blood	ACD (yellow)	6 mL (4)	X	X	X	X	X	At progression	No	Kool-pak

14.2 Collection and Processing:

14.21 Samples are to be shipped the same day as they are collected. No processing is required at the sites.

14.3 Shipping and Handling

14.31 Kits

14.311 Kits will be used for this study. Kits will contain supplies and instructions for collection, processing and shipping specimens

14.312 Participating sites may obtain kits by emailing: [REDACTED] Email requests should include address, contact information and number of kits being requested.

14.313 Kits will be sent via FedEx Ground at no additional cost to participating sites. Allow 3-4 business days to receive kits.

14.32 Shipping

Bone marrow and blood samples can be shipped with Kool Pak the same day they are collected (Monday-Thursday). They should be shipped priority overnight taking care to avoid Friday collection and shipping.

If unavoidable, Friday shipping with Saturday delivery can be arranged contacting the laboratory **in advance**.

Please notify Mayo Clinic by email [REDACTED] or phone [REDACTED] to notify laboratory when specimens are being shipped.

[REDACTED]

14.4 Background and Methodology

14.41 PDL1 expression

PDL1 expression will be measured on the myeloma cells in the bone marrow (CD138, 38 positive) by using flow cytometry. The expression will also be determined on other cell types in the bone marrow.

14.42 Measures of immune activation

The “global” impact of therapy on immune cell subsets will be ascertained by immunophenotypic analysis of PBMCs for subsets of T, B, NK cells, monocytes and dendritic cells (DC) and their activation status using commercially available monoclonal antibodies directed at the following antigens: CD3, CD4, CD8, CD11c, CD14, C16, CD19, CD20, CD25, CD45RA/RO, CD56, CD69, CD63L, CD80, CD83, CD86, CD123, DR. The flow cytometric analysis will also be performed on the bone marrow samples.

Activation of DC and subsequent modulation of the immune response caused by treatment with lenalidomide may directly or indirectly alter the cytokines present in plasma. The BioRad human 27-plex cytokine panel will be used for the measurements of plasma concentrations of IL-1 β , IL-1 α , IL-2, IL-4, IL-5, IL-6, IL-7, IL-8, IL-9, IL-10, IL-12(p70), IL-13, IL-15, IL-17, basic FGF, eotaxin, G-CSF, GM-CSF, IFN- γ , IP-10, MCP-1, MIP-1 α , MIP-1 β , [REDACTED] PDGF, RANTES, TNF- α , and VEGF.

14.43 Samples for future studies

An aliquot of CD138 sorted MM cells and CD138 negative cells will be stored for future studies. An aliquot of peripheral blood plasma as well as white blood cells (WBC) will be stored for potential studies in future.

